## Early Withdrawal From the Study

If a subject is lost to follow-up, or is unwilling to have a remote assessment performed, the subject will be considered an early withdrawal. Sites will be reminded to follow the procedures outlined in the protocol.

#### **Protocol Deviations**

All COVID-19 related protocol deviations will be reported and will be summarized in the Clinical Study Report.

WHO World Health Organization

1. INTRODUCTION

This Statistical Analysis Plan (SAP) describes the Week 96 analysis that will be performed after the last subject enrolled in the open-label extension phase completes the Week 96 visit, or prematurely discontinues from the study. The final analysis will be described in a separate SAP.

1.1. Trial Objectives

The primary objective of this study was to demonstrate non-inferiority in efficacy of a D/C/F/TAF FDC tablet versus DRV/COBI FDC co-administered with FTC/TDF FDC in HIV-1 infected, ARV treatment-naïve adult subjects, as determined by the proportion of virologic responders defined as having HIV-1 RNA <50 copies/mL at Week 48 (FDA-defined Snapshot analysis), with a maximum allowable difference of 10%.

The secondary objectives of this study were:

- To evaluate superiority of a D/C/F/TAF FDC tablet versus DRV/COBI FDC co-administered with FTC/TDF FDC as determined by the proportion of virologic responders defined as having HIV-1 RNA <50 copies/mL at Week 48 (FDA-defined Snapshot analysis), in case non-inferiority is established;
- To evaluate the immunologic response (CD4+ cell count) of the 2 treatment arms through Week 48;
- To evaluate the incidence of grade 3 and 4 AEs, serious adverse events (SAEs), and premature discontinuations due to AEs in the 2 treatment arms through Week 48;
- To evaluate the change from baseline in serum creatinine, eGFR_{creatinine} (by Cockcroft-Gault and by Chronic Kidney Disease Epidemiology Collaboration [CKD-EPI] formulas) and eGFR_{cystatin C} (by CKD-EPI) in the 2 treatment arms at Week 48;
- To evaluate the change from baseline in renal biomarkers at Week 48;
- To assess the development of viral resistance in the 2 treatment arms through Week 48;
- To evaluate the steady-state pharmacokinetics of DRV and TAF;

Objectives of a bone investigation sub-study performed at selected study sites:

- To evaluate the safety in the 2 treatment arms as determined by the percentage change from baseline in hip and spine BMD and change from baseline in T-score at Week 48;
- To evaluate the change from baseline in bone biomarker levels at Week 48.

The secondary objectives to be assessed in the study single arm treatment phase:

- To evaluate long-term safety, resistance, and efficacy of the D/C/F/TAF regimen (until Week 96 and beyond);

1.2. Trial Design

This is a randomized, double-blind active-controlled, multicenter, Phase 3 study to evaluate efficacy and safety of D/C/F/TAF once daily fixed dose combination regimen versus a regimen consisting of DRV/COBI FDC combined with FTC/TDF FDC in ARV treatment-naïve HIV-1 infected adult subjects.

The aim of this study was to include 670 subjects that were to be randomly assigned with 335 subjects planned per treatment group. Subjects who met all eligibility criteria were randomized in a 1:1 ratio to 1 of the following 2 treatment arms:

- D/C/F/TAF Arm: Regimen of a single tablet containing DRV 800 mg/ COBI 150 mg/

FTC 200 mg/ TAF 10 mg (D/C/F/TAF FDC) once daily, (n=335)

+ DRV/COBI FDC-matching and FTC/TDF FDC-matching placebo tablets

once daily;

- Control Arm: Regimen of DRV 800 mg/ COBI 150 mg FDC coadministered with FTC

200 mg/TDF 300 mg FDC once daily, (n=335)

+ D/C/F/TAF FDC-matching placebo tablet once daily.

Randomization was stratified by HIV-1 RNA level (\leq 100,000 copies/mL or \geq 100,000 copies/mL) and by CD4+ cell count (\leq 200 cells/ μ L or \geq 200 cells/ μ L) at screening.

Subjects will be treated for 96 weeks, and will return for study visits at Weeks 2, 4, 8, 12, 24, 36, 48, every 12 weeks thereafter until and including a Week 96 visit.

After Week 48, subjects will continue to take their blinded study drug and attend visits every 12 weeks until all subjects have reached Week 48, the database for the primary analysis has been locked, and treatment assignments have been unblinded. Provided the results from the primary analysis do not preclude (further) exposure of subjects to D/C/F/TAF, all subjects will return for an unblinding visit and will receive the D/C/F/TAF FDC tablet treatment during an open-label single-arm treatment phase up to Week 96. Subjects from the control arm who switch to the D/C/F/TAF regimen after the 48-week double-blind treatment will be required to return to the clinic for an additional visit 3 to 7 weeks after the unblinding visit.

After Week 96, subjects will be given the opportunity to continue D/C/F/TAF treatment during an extension phase until the D/C/F/TAF FDC tablet becomes commercially available and is reimbursed, or can be accessed through another source in the country where he/she is living, or until the sponsor terminates clinical development. During the extension phase subjects will attend visits every 6 months.

Subjects who prematurely discontinue, either during the double-blind treatment phase (from Day 1 to Week 48) or during the single-arm D/C/F/TAF phase (between Week 48 and Week 96) will be required to return to the clinic within 72 hours of stopping study treatment for the early study treatment discontinuation (ESTD) visit.

In addition, a 30-day follow-up (FU) visit will be required for any subject who has an ongoing AE or serious adverse event (SAE) at the time of his/her last study visit (unless consent is withdrawn).

Thus, the study consists of a screening period of approximately 30 days (up to maximum 6 weeks) starting from the signature of the informed consent form (ICF), double-blind active controlled treatment for at least 48 weeks, an open-label single-arm D/C/F/TAF treatment up to Week 96 and an extension phase. A 30-day FU visit may take place as described above.

The primary analysis of this study will be performed when all subjects have completed the Week 48 visit or discontinued earlier. An additional analysis will be performed when all subjects have completed the Week 96 visit. The final analysis will be performed once all subjects have completed the extension phase (and the 30-day FU visit if applicable), or discontinued earlier.

The safety and tolerability, as well as efficacy, of the enrolled subjects and treatment regimens will be monitored by an independent Data Monitoring Committee (DMC). Refer to Section 11.8 of the protocol for details. In addition to the Week 48, Week 96, and final analyses, formal DMC analyses will be performed for monitoring purposes, including a futility analysis for lack of (non-inferior) efficacy and a blinded sample size re-estimation.

A diagram of the study design is provided in Figure 1.

	eline ay 1) ^a		ek 24 MC ^b		eek 48 ^{c,d} ary analysis	Week 96 ^e Analysis	
(Da	(y 1)	Dr		1 11111		Allalysis	
Screening	Doub	le-Blind	Treatment Phase	e f	Single-arm Treatment Phase ^{c,d,f}	Extension Phase ^e	Follow-up
≤ 30 days prior to baseline	FDC- matching p Treatment a DRV/COB FTC/TDF FDC once	FFDC ond I FDC-ma lacebo tab orm 2 (Co I FDC cool daily g		ı	D/C/F/TAF FDC	D/C/F/TAF FDC	ESTD ^f and 30-day FU visit ^h

Figure 1: Schematic Overview of the Study

1.3. Statistical Hypotheses for Trial Objectives

The primary efficacy endpoint of this study was the proportion of subjects who have HIV-1 RNA <50 copies/mL at Week 48 as defined by the FDA Snapshot analysis. Thus, no formal statistical hypothesis is to be tested in the Week 96 SAP.

1.4. Sample Size Justification

A sample size of 670 (335 subjects in D/C/F/TAF arm and 335 subjects in the control arm) will yield 90% power. It was assumed that both treatment arms have a response rate of 80% (HIV-1 RNA <50 copies/mL at Week 48 as defined by the FDA snapshot analysis), that the non-inferiority margin is 10%, and that the significance level of the test is at a 1-sided, 0.025 level.

^a Following the baseline visit, subjects will return for study visits at Weeks 2, 4, 8, 12, 24, 36, 48, and every 12 weeks thereafter until and including a Week 96 visit.

^b Formal DMC interim analyses will be performed for monitoring purposes, including a futility analysis for lack of non-inferior) efficacy and a blinded sample size re-estimation.

^c Subjects will continue to take their blinded study drug and to attend visits every 12 weeks following Week 48 until treatment assignment is unblinded.

d After unblinding, provided the results from the primary analysis do not preclude (further) exposure of subjects to D/C/F/TAF, all subjects will receive D/C/F/TAF treatment during a single-arm treatment phase up to Week 96. Subjects from the control arm who switch to the D/C/F/TAF regimen after the 48-week double blind treatment will be required to return to the clinic for an additional visit 3 to 7 weeks after the unblinding visit.

^e After Week 96, subjects will be given the opportunity to continue D/C/F/TAF treatment during an extension phase until the D/C/F/TAF FDC tablet becomes commercially available and is reimbursed, or can be accessed through another source in the country where he/she is living, or until the sponsor terminates clinical development. During the extension phase subjects will attend visits every 6 months.

f Subjects who prematurely discontinue, either during the double-blind treatment phase (from Day 1 to Week 48) or during the single-arm D/C/F/TAF treatment phase (between Week 48 and Week 96) will be required to complete the ESTD assessments within 72 hours of stopping study treatment.

^g All study drugs and matching placebo tablets must be administered orally, once daily in the morning with food, at approximately the same time each day.

^h Any subject who has an ongoing AE or SAE at the time of his/her last study visit will be required to return to the clinic 30 days after the completion their his/her study visit for a 30-day FU visit (unless consent is withdrawn).

A minimum of 170 subjects (85 per treatment arm) was targeted to be included in the bone investigation sub-study. Assuming a 4% inter-subject variability in BMD and a 1-sided alpha level of 2.5%, 85 subjects per treatment arm is sufficient to detect at least an absolute difference of 2% between the treatment arms with 90% power. Power calculations are presented in Table 1.

Table 1:	BMD at the Lumbar Spine, Power Calculations
----------	---

	Mean % Change from	Common Standard	Power
	Baseline	Deviation (%)	
	2	3.5	96%
N=170	4	4	90%
IN-170	3	3.5	>99%
	3	4	>99%

1.5. Randomization and Blinding

Randomization

Central randomization was implemented in conducting this study. Subjects were assigned to 1 of 2 treatment groups in a 1:1 ratio based on computer-generated randomization schedule implemented in the interactive web response system (IWRS) before the study. Randomization minimizes the imbalance in the distribution of the number of subjects across treatment groups within the levels of each individual stratification factor: HIV-1 RNA level ($\leq 100,000$ copies/mL or > 100,000 copies/mL) and CD4+ cell count (< 200 cells/ μ L or ≥ 200 cells/ μ L) at screening. Based on the algorithm, the IWRS assigned a unique treatment code, which dictated the treatment assignment and matching study drug kit for the subject.

Blinding

Subjects continued to take their blinded study drug and to attend visits every 12 weeks following Week 48 until treatment assignment was unblinded. After unblinding, all subjects will receive D/C/F/TAF treatment during a single-arm treatment phase up to Week 96. Subjects from the control arm who switch to the D/C/F/TAF regimen after the 48-week double blind treatment were required to return to the clinic for an additional visit 3 to 7 weeks after the unblinding visit.

2. GENERAL ANALYSIS DEFINITIONS

2.1. Treatment Arms

Following notations for the treatment arms in the single arm treatment phase will be used:

- **Initial D/C/F/TAF Arm**: subjects who received D/C/F/TAF FDC treatment at baseline of the treatment phase
- Late Switch to D/C/F/TAF Arm: subjects who were on DRV/COBI FDC+ FTC/TDF FDC treatment and switched to D/C/F/TAF treatment during the single arm treatment phase

2.2. Visit Windows

2.2.1. Trial Phases

Phases will be constructed for each subject as follows for adverse events, concomitant therapies, and for the determination of the worst-case/toxicity/change in the cross-tabulations.

Trial phase	Start date	End date
Screening	Minimum of Date of signing the informed consent and Date of the screening visit	1 day before start of treatment
Comparative	Date of the first intake (after	For ongoing subjects, in order of priority:
Treatment Phase	randomization)	- Week 48 visit date;
		if missing then;
		 Projected Week 48 visit date, where projected Week 48 visit date = baseline visit date + (7 *48)
		In case of withdrawal use:
		 Minimum(last intake date of study drug, study withdrawal date) +2 days
	Comparative treatment phase	If a subject switches prior to Week 96:
	end date +1 day	 Minimum(Date of last double-blind intake +2 days, Start Date of first Open Label D/C/F/TAF intake)
		If a subject never switches prior to Week 96:
		- Week 96 visit date;
		if missing then;
		 Projected Week 96 visit date, where projected Week 96 visit date = baseline visit date + (7 *96)
		In case of withdrawal prior to switching use:
		Minimum (last intake date of study drug, study withdrawal date) + 2 days
Single Arm	Extended double-blind	- Week 96 visit date;
treatment phase (Switch	treatment phase end date +1 day	if missing then;
to Week 96) *		 Projected Week 96 visit date, where projected Week 96 visit date = baseline visit date + (7 *96)
		In case of withdrawal after switch use:
		 Minimum (last intake date of study drug, study withdrawal date) + 2 days
Follow-up	Maximum (end date of extended double-blind treatment phase, end date of single arm treatment phase) +1 day	Trial termination date for all groups (date of last contact)

^{*} The 3-7 WEEKS AFTER UNBLINDING visit will be handled as follows:

Data up to each subject's Week 96 visit are in scope for this analysis; in addition DXA data (DP domain) up to Week 96 visit+28 days, and if applicable, any (confirmatory) viral load or genotype/phenotype results immediately subsequent to Week 96 (up to 6 weeks) will also be included in this analysis.

⁻ All efficacy assessments collected at this visit will be attributed to the DRV/COBI FDC + FTC/TDF FDC regimen

⁻ All safety assessments collected at this visit will be attributed to the D/C/F/TAF FDC regimen

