### - Control Arm (n=335):

Regimen of DRV 800 mg/ COBI 150 mg FDC coadministered with FTC 200 mg/ TDF 300 mg FDC once daily

+ D/C/F/TAF FDC-matching placebo tablet once daily.

All baseline tests and procedures must be completed prior to the administration of the first dose of study treatment. Initiation of study treatment must take place within 24 hours after the baseline visit.

The investigational medication, D/C/F/TAF FDC tablets, the control DRV/COBI FDC tablets and the D/C/F/TAF FDC- and DRV/COBI FDC-matching placebo tablets (identical in physical appearance), will be manufactured, packaged and provided by the sponsor. The control FTC/TDF FDC tablets and matching placebo tablets will be manufactured, packaged by GSI and provided to the sponsor for distribution.

Study-site personnel will instruct subjects on how to store study drug for at-home use as indicated for this protocol.

All study drugs and matching placebo tablets must be administered orally, once daily in the morning with food, at approximately the same time each day. Study drugs should be taken on site with food during study site visits (except Week 8 and Week 36), after all safety assessments that require fasting are taken. If subjects notice that they missed a medication intake and it is still within 12 hours of their regular dosing time, they should take the medication immediately with food. Subjects can then continue their usual dosing schedule. If subjects notice that they missed their dose >12 hours after the time it is usually taken, they should be instructed not to take it and simply resume the usual dosing schedule. Subjects should not take a double dose to make up for a missed dose.

Prolonged temporary study treatment interruptions are only deemed acceptable if motivated by safety reasons and do not last longer than 4 consecutive weeks. The sponsor should be notified when such temporary interruption occurs.

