5. SAFETY

For initial D/C/F/TAF, periods "Baseline to Week 48", "Week 48 to Week 96" and "Baseline to Week 96" will be presented in the tables. For the late switchers, periods "Baseline to Switch" and "Switch to Week 96" will be presented.

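### For a prompt switch, SAP 2.2.1 leaves the first open-label D/C/F/TAF day in the pre-switch phase, so in the Late Switch arm adverse events starting that day count under the comparator.

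*SAP*

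**What the plan says.** SAP 2.2.1 defines date-based phases and says what they are for: "Phases will be constructed for each subject as follows for adverse events, concomitant therapies", as well as worst-case values in the cross-tabulations. For a subject who switches before Week 96, the extended double-blind phase ends at "Minimum(Date of last double-blind intake +2 days, Start Date of first Open Label D/C/F/TAF intake". The single-arm phase starts at the extended double-blind "treatment phase end date +1 day", so the end date itself belongs to the earlier phase.

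At study start the table works the other way. Screening ends "1 day before start of treatment", and the comparative phase opens on the date of first intake.

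SAP 2.1 defines the Late Switch arm as "subjects who were on DRV/COBI FDC+ FTC/TDF FDC treatment and switched to D/C/F/TAF treatment during the single arm treatment phase". SAP 5 then fixes the safety reporting periods: "For the late switchers, periods 'Baseline to Switch' and 'Switch to Week 96' will be presented". For the other arm the switch is not a boundary: "For initial D/C/F/TAF, periods 'Baseline to Week 48', 'Week 48 to Week 96' and 'Baseline to Week 96' will be presented".

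On timing, Protocol Section 6 states: "All study drugs and matching placebo tablets must be administered orally, once daily in the morning with food". The footnotes to the Time and Event Schedule have subjects stop blinded drug and move to D/C/F/TAF at the unblinding visit, where open-label drug is first dispensed. No washout is described.

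**The concern.** For a subject who changes tablets without a break, the end-date rule returns the first open-label date itself. That day is therefore assigned to the phase of the regimen just stopped. In the Late Switch arm the two phases correspond to different regimens, and safety is tabulated on either side of the switch. An event that starts on the first day of D/C/F/TAF is counted against DRV/COBI + FTC/TDF.

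For these prompt switches the shift goes one way: it can only raise the pre-switch count and lower the post-switch count, in favour of the test regimen. The events most exposed are acute reactions on starting a tablet, such as nausea, vomiting or hypersensitivity, all of which are on the SAP's list of adverse drug reactions (Attachment 3). The SAP gives no reason for departing from its own first-intake convention. The footnote to the phase table that assigns safety data to D/C/F/TAF concerns only the visit 3 to 7 weeks after unblinding, so it does not correct the first day.

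**Working it through.** The plan states no figure on this point, so there is none to reproduce. The check is date arithmetic on the SAP 2.2.1 rule.

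**Inputs.** Set the last double-blind intake at day 0 and the first open-label intake at day g.

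- Extended double-blind end = min(0 + 2, g) = min(2, g) (SAP 2.2.1).
- Single-arm start = that end + 1 (SAP 2.2.1).
- Expected g is about 1, from once-daily dosing (Protocol Section 6) and direct changeover at the unblinding visit (Time and Event Schedule footnotes).

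The last two columns replace g by g − 1 in the second term, giving an end of min(2, g − 1).

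| g (days) | End, current | Start, current | First open-label day falls in | Start minus g | End, amended | Start, amended |
|---|---|---|---|---|---|---|
| 0 | 0 | 1 | double-blind | +1 | −1 | 0 |
| 1 | 1 | 2 | double-blind | +1 | 0 | 1 |
| 2 | 2 | 3 | double-blind | +1 | 1 | 2 |
| 3 | 2 | 3 | single-arm | 0 | 2 | 3 |
| 4 | 2 | 3 | single-arm | −1 | 2 | 3 |
| 5 | 2 | 3 | single-arm | −2 | 2 | 3 |

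**Reading the table.** Under the current rule the single-arm phase starts one day late for g = 0, 1 or 2 and on time for g = 3. For g of 4 or more it starts g − 3 days before the first open-label dose. Under the amended rule it starts on the first open-label day for every g from 0 to 3. For larger gaps nothing changes. At g = 0, where both intakes share a date, that whole date moves to the single-arm phase.

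**Size.** At most one day per late switcher. If all 335 planned control subjects switched with g of 2 or less, that is 335 person-days, or 335 / 365.25 = 0.92 person-years. The length of the single-arm period varies by subject and is not given. For an assumed 12 weeks, one day is 1/84 = 1.2% of it; for an assumed 47 weeks, 1/329 = 0.3%. The documents do not allow an estimate of how many adverse events start on the switch date.

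**Which data are affected.** Open-label drug is first dispensed at the unblinding visit, and Protocol Section 6 has on-site dosing follow the fasting safety assessments. There are two cases.

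- The first open-label tablet is taken at the visit. The fasted samples then precede it and belong to the old regimen, where the current rule puts them. SAP 2.6 takes the last value before the switch as the post-switch reference, and that is normally this visit's value.
- The first open-label tablet is taken the next day. No visit is then scheduled on that day.

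Neither case produces a scheduled fasted laboratory value that is wrongly placed. For vital signs, the order relative to dosing is not stated.

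**The case against.** The strongest reply is that any whole-day boundary is a convention. With dates only, an event starting on the switch date may precede the dose, for example one reported at the unblinding visit, and would then be correctly placed before the switch. The study-start comparison is also imperfect, because SAP 2.2.2 has a separate rule that picks out the baseline record and the switch has no such analysis time point. Late switchers already take darunavir, cobicistat and emtricitabine at the same doses, with only TDF replaced by TAF, so few first-day reactions may be expected. Adverse events are not formally tested (SAP 5.1.2).

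This stands as a limit on importance. It does not remove the inconsistency: the same before-or-after-dose ambiguity exists on Day 1, and there the SAP gives the day to the new treatment.

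Three stronger readings are tempting and are not supported.

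- A reader might infer that laboratory and vital-sign worst values are displaced in the same way. The visit order contradicts this for fasted samples, and for vital signs it is not shown.
- A reader might infer that the bias always favours D/C/F/TAF. With a gap of 4 days or more, the single-arm phase opens before the first open-label dose, so events in those gap days go to D/C/F/TAF.
- A reader might infer that every switch-date event is charged to the wrong regimen. Some will have begun before the dose.

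**Conclusion.** The point holds for adverse events, and for concomitant therapies assigned by date. For gaps of 2 days or less, SAP 2.2.1 puts the first D/C/F/TAF day in the pre-switch phase, contrary to the SAP's own rule at study start. The consequence is confined to the Late Switch arm: in the Initial D/C/F/TAF arm both phases are the same regimen and the safety periods are not divided at the switch. The effect is at most one day per late switcher (0.92 person-years at the planned maximum), and no conclusion of the trial is shown to depend on it. It is a minor correction.

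This rests on two assumptions. One is that adverse events are assigned by onset date, which is inferred from the phase table because the SAP defines treatment-emergent only for vital signs. The other is that most subjects switch with a gap of about a day, which the dosing schedule and visit procedures imply but the documents do not report.

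**What to change.** In SAP 2.2.1, for adverse events and concomitant therapies, end the extended double-blind phase at the earlier of (last double-blind intake + 2 days) and (first open-label D/C/F/TAF intake date − 1 day). For gaps of up to 3 days the single-arm phase then opens on the first open-label intake date.

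Add a sentence that laboratory and vital-sign assessments taken at the unblinding visit before the first open-label dose stay in the pre-switch phase and serve as the post-switch reference under SAP 2.6. Without it, the changed date would pull pre-dose results into the D/C/F/TAF phase.

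The cost is one term in the table, one clarifying sentence and the matching programming. There is a small downside: a switch-date event that began before the dose would be counted under D/C/F/TAF, as already happens on Day 1. The edit leaves gaps of 4 days or more as they are. If the current rule is intended, the SAP should say why.

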Any subjects who have an eGFRcreatinine (by Cockcroft-Gault) <50 mL/min, and who also experience >20% reduction in eGFRcystatin (by CKD-EPI) from baseline, or who have other clinical and/or laboratory evidence of acute renal failure will be discussed with the sponsor's medical monitor and may permanently discontinue study drugs. For subjects with eGFRcreatinine <50 mL/min who are not discontinued based on toxicity management procedures above and considered to have stable renal function per principal investigator and medical monitor, it is not mandatory to repeat eGFR assessments within 3 days.

All subjects with negative or trace proteinuria at baseline who develop >1+ proteinuria on urinalysis must have a urinalysis repeated, with a concurrent urine chemistry, within 2 weeks of receipt of results. Upon confirmation of proteinuria, subjects will be asked to return to the clinic for a scheduled or unscheduled FU visit. It is recommended that the investigator contacts the sponsor's medical monitor to discuss if further consultation with a nephrologist is clinically warranted.

Once an individual subject has developed any of these renal changes and the above management guidelines have been applied, it is not necessary to further unscheduled repeat evaluations if it is determined that it is safe for the subject to continue on treatment with standard visits as described in the protocol.

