5.2.3.2. Proximal Renal Tubular Function

Proteinuria by Quantitative Assessment

Total urine protein, total urine albumin, urine protein to creatinine ratio (UPCR) and urine albumin to creatinine ratio (UACR) will be summarized by treatment arm and visit using descriptive statistics.

The number and proportion of subjects with UACR and UPCR results in the following categories at Week 96 will be tabulated:

- UACR: $< 30, \ge 30 \text{ to } 300, >300 \text{ mg/g}$
- UPCR: $< 200 \text{ mg/g versus} \ge 200 \text{ mg/g}$

Median (Q1, Q3) percent change from reference over time will be plotted by treatment group.

The evolution over time of total urine protein and total urine albumin will also be presented.

Proteinuria by Urinalysis (Dipstick)

Treatment-emergent proteinuria by urinalysis (dipstick) through Week 96 will be summarized by treatment group. Cross-tabulation of grades at Week 96 versus reference will also be presented.

Other Renal Biomarkers

Selected renal biomarkers retinol binding protein (RBP) and beta-2-microglobulin, RBP to creatinine ratio and beta-2-microglobulin to creatinine ratio will be summarized by treatment arm and visit using descriptive statistics. The proportions of subjects with beta-2-microglobulin to creatinine ratio <=300 mg/g and >300 mg/g will be tabulated.

The number and proportion of subjects with retinal binding protein to creatinine ratio results in the following categories at Week 96 will be tabulated:

• < 50 years of age (at the time of lab assessment): < 130 mcg/g creatinine, \geq 130 mcg/g creatinine

• \geq 50 years of age (at the time of lab assessment): \leq 172 mcg/g creatinine, \geq 172 mcg/g creatinine

Phosphate excretion

Other renal biomarkers include urine fractional excretion of phosphate (FEPO4) that will be summarized by treatment arm and visit using descriptive statistics.

Urine fractional excretion of Phosphate (FEPO4) will be calculated as follows:

• Based on unadjusted serum creatinine:

$$FEPO4 (\%) = (SCr \times UPO4) / (SPO4 \times UCr) \times 100 (\%)$$

The reference, post-reference, and change from reference in FEPO4 will be summarized by treatment arm and visit using descriptive statistics. Median (Q1, Q3) change from baseline in FEPO4 over time will be plotted by treatment group.

Subclinical renal proximal tubulopathy

Potential Markers of Renal Proximal Tubulopathy are:

- 1. Increase in serum creatinine ≥ 0.40 mg/dL from reference.

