- 2. Confirmed ≥ 2 grade level increase from reference in graded proteinuria
- 3. Confirmed ≥ 1 grade level increase from reference in graded hypophosphatemia
- 4. Confirmed ≥ 1 grade level increase from reference in graded glycosuria concurrent with serum glucose <=100 mg/dL (normoglycemic glycosuria)

A confirmed laboratory abnormality is defined as an abnormality observed at 2 consecutive postreference measurements or an abnormality observed at 1 measurement followed by study drug discontinuation

A subclinical renal proximal tubulopathy will be defined as confirmed abnormalities in any 2 out of the 4 renal parameters (serum creatinine and one or more of the 3 other markers of tubular dysfunction).

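### The Week 96 data cut makes no allowance for renal laboratory retests, so for subjects who stay on drug a tubular marker first abnormal at Week 96 cannot be confirmed and the confirmed counts are truncated downward

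*SAP*

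**What the plan says.** **Scope.** SAP 2.2.1 states: "Data up to each subject's Week 96 visit are in scope for this analysis". It then lists two additions. One is "in addition DXA data (DP domain) up to Week 96 visit+28 days". The other is "any (confirmatory) viral load or genotype/phenotype results immediately subsequent to Week 96 (up to 6 weeks) will also be included in this analysis". Renal and other laboratory retests are not mentioned.

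**Confirmation.** SAP 5.2.3.2 defines a confirmed laboratory abnormality as "an abnormality observed at 2 consecutive postreference measurements or an abnormality observed at 1 measurement followed by study drug discontinuation". The proteinuria, hypophosphatemia and normoglycemic glycosuria markers each carry the word confirmed. The creatinine marker reads only "Increase in serum creatinine ≥ 0.40 mg/dL from reference". The composite, however, is worded for all four: "A subclinical renal proximal tubulopathy will be defined as confirmed abnormalities in any 2 out of the 4 renal parameters", with creatinine as one of the two.

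**Retests in the protocol.** Under Protocol 9.5.4, subjects whose dipstick protein rises from negative or trace at baseline to above 1+ "must have a urinalysis repeated, with a concurrent urine chemistry, within 2 weeks of receipt of results". The same section calls for creatinine to be re-measured when creatinine-based eGFR is below 50 mL/min. Protocol 9.4.2 asks for grade 3 or 4 laboratory results to be repeated, preferably within 72 hours.

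**Other scope statements.** SAP 2.2.2 runs the Week 96 window from Day 631 to Day 714. SAP 2.3.2 says the safety analysis takes in data through the 30-day follow-up visit. Neither is reconciled with 2.2.1.

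**The concern.** The cut-off and the definition of confirmation do not fit together at the last visit. A subject who continues drug and shows a marker for the first time at Week 96 has no second in-scope value. The next scheduled visit, in the extension phase, is about 6 months away. The plan recognises this problem for viral load and allows 6 weeks for a confirmatory result. Protocol 1.7 names renal and bone toxicity as the primary nonclinical toxicities of TAF; bone imaging receives an allowance in 2.2.1 and renal laboratory data do not.

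The truncation is also uneven. SAP 2.6 resets the Late Switch reference to the last value before the switch, and SAP 5 reports the period from switch to Week 96 separately. Fewer visits fall in that period, so the last one carries a larger share of the opportunities for a first abnormality. A low confirmed count on D/C/F/TAF after the switch would partly reflect short follow-up with no chance to confirm.

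**Working it through.** The documents state no rate or count for tubulopathy, so there is no figure of the plan's own to reproduce. The check is a visit count.

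**Inputs**
- Scheduled post-baseline visits to Week 96 (SAP 1.2): Weeks 2, 4, 8, 12, 24, 36, 48, 60, 72, 84, 96, which is 11. The Time and Event Schedule has chemistry and urinalysis at all of them.
- Former control subjects have one extra visit 3 to 7 weeks after unblinding (SAP 1.2).
- Assumptions: the switch falls at Week 60, 72 or 84 (no switch-time distribution is given), and first onsets are spread evenly over the scheduled visits of the period.

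**Formula.** A first abnormality at visit k needs visit k+1 in scope. With m in-scope visits only the last fails, so the unconfirmable share of visits is 1/m.

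| Arm and period | Visits (m) | Share 1/m |
|---|---|---|
| Initial, Baseline to Week 96 | 11 | 1/11 = 9.1% |
| Initial, Week 48 to 96 | 60, 72, 84, 96 (4) | 1/4 = 25% |
| Late Switch, switch at 60 | extra, 72, 84, 96 (4) | 1/4 = 25% |
| Late Switch, switch at 72 | extra, 84, 96 (3) | 1/3 = 33% |
| Late Switch, switch at 84 | extra, 96 (2) | 1/2 = 50% |

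Protocol 9.1.4 lets the extra visit be merged with a planned visit within 4 weeks of it. m then drops by one and the Late Switch shares become 1/3, 1/2 and 1/1. A switch exactly on a planned week puts the extra visit 12 − 7 = 5 to 12 − 3 = 9 weeks before the next planned visit, so merging needs visits off their nominal dates.

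**Sensitivity: onset even over time instead of over visits.** The share is the last interval divided by the period length.
- Initial, Baseline to Week 96: 12/96 = 12.5%. Week 48 to 96: 12/48 = 25%.
- Late Switch at Week 60: 12/36 = 33%. At Week 72: 12/24 = 50%.
- Late Switch at Week 84: from (96 − 91)/12 = 42% to (96 − 87)/12 = 75%, depending on when the extra visit occurs.

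Under either assumption these are ceilings on cases lost. Some abnormalities would not persist on retest, and some count through discontinuation.

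**Would a retest fit the window?** The Week 96 target is Day 673 and the window closes on Day 714, so 714 − 673 = 41 days, about 6 weeks. A prompt retest falls inside the SAP 2.2.2 window yet outside the 2.2.1 scope sentence.

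**Would the protocol produce one?** For proteinuria, often. A subject with a negative baseline who reaches 2+ (grade 2 in Protocol Attachment 1) meets both the protocol's retest trigger and the SAP's marker of a rise of at least two grades. For the other markers, less often. Nothing in the retest rules above is triggered by a 0.40 mg/dL creatinine rise with eGFR still at or above 50, or by grade 1 or 2 hypophosphatemia or glycosuria.

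**The case against.** The strongest reply is that little is hidden. SAP 5.2.2 tabulates worst toxicity grades through and at Week 96 and lists abnormal values. SAP 5.2.3.2 reports treatment-emergent dipstick proteinuria, UACR and UPCR categories, and the RBP and beta-2-microglobulin ratios. None of these requires confirmation, so an abnormality first seen at Week 96 appears in them. The composite is not among the protocol's listed endpoints (Protocol 11.1), SAP 1.3 tests no formal hypothesis at Week 96, and SAP 3.4 shows exposure after the switch. All of this stands and limits the point to the confirmed markers and the composite.

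SAP 2.3.2 may also seem to bring later safety data in. It helps only in part. Protocol 9.1.6.2 requires the 30-day visit only for subjects with an ongoing AE or SAE at their last study visit, and a subject entering the extension has not had a last visit. Extension data may reach the final analysis, but that has its own SAP, so the gap is established for this data cut only.

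A reader might infer that a Week 96 abnormality can never count, or that the rate is zero by construction for anyone with a single post-switch value. The documents do not support that. One abnormal measurement followed by stopping drug also confirms, although the SAP does not say whether a discontinuation after the Week 96 visit is in scope. An unscheduled abnormal result shortly before the Week 96 visit can be confirmed at that visit. Nor should the shares be read as cases lost, or 25% be quoted for the Initial arm without the 1/11 for the Baseline to Week 96 period that the SAP also reports.

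**Conclusion.** The gap is real and narrow. In this data cut, a subject who stays on drug and first shows a marker at the Week 96 visit cannot meet the two-measurement route, so the confirmed-marker and subclinical tubulopathy counts can only be lowered. The ceiling is 1/11 or 1/4 of scheduled visits in the Initial arm, depending on the period. It is 1/4 to 1/2 after the switch in the Late Switch arm, and more if the extra visit is merged. These figures rest on assumed switch weeks and even onset over visits. The effect on the counts themselves cannot be computed, because the documents give neither an event rate nor the persistence of abnormalities on retest.

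It would go too far to infer that renal safety reporting as a whole is biased low: the summaries that need no confirmation are untouched. What remains is an avoidable truncation in a descriptive count. It falls more heavily on the post-switch period and is worth a cheap correction.

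**What to change.** 1. In SAP 2.2.1, extend the confirmatory exception (up to 6 weeks) to any available renal laboratory retest after an abnormal Week 96 result: serum creatinine, phosphate and glucose, and urine dipstick and chemistry.
2. Reconcile 2.2.1 with the Day 714 window in 2.2.2 and the 30-day follow-up scope in 2.3.2. State that confirmation uses all in-scope measurements, because 2.2.2 otherwise keeps one value per time point for displays. Say whether a discontinuation after the Week 96 visit counts.
3. In 5.2.3.2, add a row by arm and period for markers first abnormal at the last in-scope visit with no retest, labelled as unconfirmed at last visit. State whether the creatinine marker itself needs confirmation.

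The cost is a sentence or two of scope text and one table row, with no new visits and no change to any clinical rule. Confirmed counts may rise slightly. Retests will exist only for some markers and subjects, which is why the separate row is needed alongside the wider scope.
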